5.3. Lifestyle Considerations

The following guidelines are provided:

5.3.1. Contraception

The investigator or their designee, in consultation with the participant, will confirm that the participant is utilizing an appropriate method of contraception for the individual participant and their partner(s) from the permitted list of contraception methods (see [Appendix 4, Section 10.4.3](#)) and will confirm that the participant has been instructed in its consistent and correct use. At time points indicated in [SoA](#), the investigator or designee will inform the participant of the need to use highly effective contraception consistently and correctly and document the conversation and the participant's affirmation in the participant's chart. Participants need to affirm their consistent and correct use of at least 1 of the selected methods of contraception, considering that their risk for pregnancy may have changed since the last visit.

In addition, the investigator or designee will instruct the participant to call immediately if the selected contraception method is discontinued and document the requirement to use an alternate protocol-specified method, including if the participant will no longer use abstinence as the selected contraception method, or if pregnancy is known or suspected in the participant or partner.

5.3.2. Meals and Dietary Restrictions

- Participants must abstain from all food and drink (except water) at least 4 hours prior to any safety laboratory evaluations.
- On Dosing days in periods 1 and 2, participants will consume a standard meal approximately 30 minutes prior to dosing. They should be encouraged to complete their meals on Day 1 and Day 5 (PK sampling days) by approximately 10 minutes prior to anticipated dosing.
- During Period 3, lunch will be the first meal after an overnight fast of approximately 10 hours.
- During the palatability assessment periods, there will be at least 60 minutes between meals and palatability assessments.

- Lunch will be provided approximately 4 hours after dosing.
- In Period 3, dinner will be provided approximately 13 hours after AM dosing (1 hour after PM dosing).
- In Period 3, an afternoon snack may be permitted approximately 7.5 hours after AM dosing.
- An evening snack may be permitted, for all periods.
- Participants will refrain from consuming red wine, grapefruit, or grapefruit-related citrus fruits (eg, Seville oranges, pomelos, fruit juices) from 7 days prior to the first dose of study intervention until collection of the final PK blood sample.
- While participants are confined, their total daily nutritional composition should be approximately 55% carbohydrate, 30% fat, and 15% protein. The daily caloric intake per participant should not exceed approximately 3200 kcal.

5.3.3. Caffeine, Alcohol, and Tobacco

- Participants will abstain from caffeine-containing products for 24 hours prior to the start of dosing until collection of the final PK sample of each study period.
- Participants will abstain from alcohol for 24 hours prior (or as specified above for red wine) to admission to the CRU and continue abstaining from alcohol until collection of the final PK sample of each study period. Participants may undergo an alcohol breath test or blood alcohol test at the discretion of the investigator.
- Participants will abstain from the use of tobacco- or nicotine-containing products for 24 hours prior to dosing and during confinement in the CRU.

5.3.4. Activity

- Participants will abstain from strenuous exercise (eg, heavy lifting, weight training, calisthenics, aerobics) for at least 48 hours prior to each blood collection for clinical laboratory tests. Walking at a normal pace will be permitted.
- In order to standardize the conditions on PK sampling days, participants will be required to refrain from lying down (except when required for BP, pulse rate, and ECG measurements), eating, and drinking beverages other than water during the first 4 hours after dosing. These criteria only apply to the AM doses on Days 1 and 5 (Periods 1-3).

5.4. Screen Failures

Screen failures are defined as participants who consent to participate in the clinical study but are not subsequently enrolled in the study. Screen failure data are collected and remain as source and are not reported on the CRF.

Individuals who do not meet the criteria for participation in this study (screen failure) may be rescreened.

6. STUDY INTERVENTION(S) AND CONCOMITANT THERAPY

Study interventions are all prespecified investigational and non-investigational medicinal products, medical devices, and other interventions (eg, surgical and behavioral) intended to be administered to the study participants during the study conduct.

For the purposes of this protocol, study intervention refers to sisunatovir and placebo.

6.1. Intervention(s) Administered

Study Intervention(s)			
Intervention Name	PF-07923568 (sisunatovir)	Placebo for PF-07923568 (sisunatovir)	PF-07923568 (sisunatovir) Palatability in Liquid Vehicles
Unit Dose Strength(s)	50 mg	Placebo	Content of 50 mg capsule
Dose Formulation	capsule	Capsule	Capsule content dispensed in liquid vehicles
Dosage Level(s)	Planned doses are 200 mg and 400 mg BID for 4 days plus 1 dose in Cohort 1. Doses in Cohort 2 will not exceed 400 mg Q12 hours.	0 mg	Planned doses are the content of a 50 mg capsule of sisunatovir, dispensed in 7 ml of the following liquid vehicles: 
• Water• Infant formula• Apple juice• Saline
Route of Administration	Oral	Oral	Oral/"Swirl and Spit"
Use	Experimental	Placebo	Experimental
IMP or NIMP/AxMP	IMP	IMP	IMP
Sourcing	Provided centrally by the sponsor	Provided centrally by the sponsor	Sisunatovir: Provided centrally by the sponsor Liquid vehicles: Provided locally by the CRU
Packaging and Labeling	The PF-07923568 50 mg capsules will be provided in bulk. CRU Staff will prepare individual doses for administration	The placebo capsules will be provided in bulk. CRU Staff will prepare individual doses for administration	The PF-07923568 50 mg capsules will be provided in bulk. CRU Staff will prepare individual doses (capsule content + liquid) for administration

Study Intervention(s)			
Current/former Name(s) or Alias(es)	Sisunatovir PF-07923568 RV521	Placebo	Sisunatovir PF-07923568 RV521 Liquid vehicles: As available locally.

Study intervention will be supplied by Pfizer as 50-mg capsules.

Matching placebo capsules will also be provided.

Capsules will be supplied to the CRU in bulk along with individual dosing containers for unit dosing.

6.1.1. Administration

6.1.1.1. Period 1 and 2

During Periods 1 and 2 for Cohorts 1 and 2, participants will receive study intervention at approximately 0800 hours (plus or minus 2 hours) approximately 30 minutes after the start of a standard breakfast that will be consumed over approximately 20 minutes. Participants will receive the evening dose of study intervention 12 hours after the morning dose (plus or minus 1 hour) approximately 30 minutes after the start of a standard dinner that will be consumed over approximately 20 minutes. On Day 5 in each period only the morning dose of study intervention will be administered. Investigator site personnel will administer study intervention during each period with ambient temperature water to a total volume of approximately 240 mL. Participants may receive additional ambient temperature water up to 100 mL, if needed. This will be documented by the site. Participants will swallow the study intervention whole and will not manipulate or chew the study intervention prior to swallowing.

6.1.1.2. Period 3

During Period 3 for Cohorts 1 and 2, participants will receive morning study intervention at approximately 0800 hours (plus or minus 2 hours). For the Day 1 morning and Day 5 morning doses, the pre-dose fasting period is 10 hours and post-dose fasting period is a minimum of 4 hours. For all Days 2, 3, and 4 morning doses, the pre-dose fasting period is 8 hours and the post-dose fasting period is a minimum of 1 hour. For evening doses, the pre-dose fasting period is 4 hours, and the post-dose fasting period is a minimum of 1 hour. On Day 5 only the morning dose of study intervention will be administered. For all doses, participants will have nothing to drink (including water) for 1 hour pre-dose and 1 hour post-dose. Investigator site personnel will administer study intervention during each period with ambient temperature water to a total volume of approximately 240 mL. Participants may receive additional ambient temperature water up to 100 mL, if needed. This will be documented by the site. Participants will swallow the study intervention whole and will not manipulate or chew the study intervention prior to swallowing.

On Day 1 and Day 5 for morning doses, in order to standardize the conditions on PK sampling days, all participants will be required to refrain from lying down (except when required for BP, pulse rate, and ECG measurements), eating, and drinking beverages other than water during the first 4 hours after dosing.

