1. PROTOCOL SUMMARY

1.1. Synopsis

Protocol Title:

A Phase 1, Randomized, Sponsor Open, Two-Part Crossover Study to Assess Safety, Tolerability, Pharmacokinetics and Food Effect of Multiple Doses in Part 1 and Palatability of a Single Dose of Sisunatovir in Part 2, in Healthy Adult Participants

Brief Title: A Study to Assess the Safety, Tolerability, Pharmacokinetics, Food Effect, and Palatability of Sisunatovir in Healthy Adult Participants

Regulatory Agency Identification Number(s):

US IND Number:	143479
EudraCT Number:	2022-003426-53
ClinicalTrials.gov ID:	N/A
Pediatric Investigational Plan Number:	N/A
Protocol Number:	C5241006
Phase:	1

Rationale:

Sisunatovir (PF-07923568) is an orally administered RSV F-protein inhibitor being developed to target viral-host cell fusion for the treatment of adult and pediatric patients with RSV. This study is designed to assess safety and tolerability, pharmacokinetics, and food effect of multiple oral doses of sisunatovir. Additionally, the study is also designed to generate preliminary palatability data that will inform further development of formulations appropriate for pediatric Phase 2 and 3 studies.

Objectives and Endpoints:

Objectives	Endpoints
Primary:	Primary:
• To characterize the safety and tolerability of multiple oral doses of sisunatovir in healthy adult participants	• Assessment of TEAEs, clinical laboratory abnormalities, vital signs, and 12-lead ECGs
Secondary:	Secondary:
• To characterize the PK of multiple oral doses of sisunatovir	• PK Parameters AUC_{tau} , C_{max} , T_{max} , $AUC_{\text{tau}}(\text{dn})$, $C_{\text{max}}(\text{dn})$ for Day 1 and AUC_{tau} , C_{max} , T_{max} , $AUC_{\text{tau}}(\text{dn})$, $C_{\text{max}}(\text{dn})$, CL/F , R_{ac} , $R_{\text{ac,Cmax}}$; and $t_{1/2}$ and V_z/F (if data permits) post last dose on Day 5
• To evaluate the effect of food on the PK of multiple oral doses of sisunatovir	• The ratio of AUC_{tau} and C_{max} , on Day 5; T_{max} on Day 5
• To characterize the impact of liquid vehicles on the palatability of sisunatovir	• Palatability Assessment Questionnaire Scoring Metrics: mouth feel, bitterness, sweetness, sourness, saltiness, tongue/mouth burn, overall liking

Overall Design:

This is a Phase 1 study that will be conducted in up to two cohorts.

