TEAEs were in the GI disorders SOC; nausea, diarrhea and abdominal pain. These TEAEs have been mild to moderate in intensity and resolved without sequelae. Most events attributed to IMP involved the gastrointestinal tract with nausea, diarrhea, and abdominal pain/discomfort/distension being the most common and occurring more commonly with the 350 mg dose of sisunatovir than with the 200 mg sisunatovir dose, where the number of participants reporting these events were lower and similar to those on placebo. In children, sisunatovir is required to be suspended in a solution to enable oral administration, there has been evidence of poor tolerability when sisunatovir was suspended in water as a single dose of 2.0 mg/kg in children aged 6-36 months, resulting in expulsion of the oral dose. Suspension in breast milk, formula milk or saline appeared to improve the palatability, with all doses being successfully administered to children aged 1 to 36 months in study C5241003.

As of 28 October 2022, there have been no SAEs attributable to sisunatovir and no deaths in the clinical studies.

In adults, sisunatovir is slowly absorbed reaching maximum plasma concentrations (t_{max}) at 5-6 hours (hrs) with a relatively moderate clearance, resulting in a half-life of 7-10 hours in healthy participants. Dosing to steady state resulted in steady state concentrations being reached after approximately 2 days of dosing resulting in 2-4 fold accumulation of exposure. AUC and C_{max} values increased in a greater than dose proportional manner across single and multiple dose studies. Following 5 days of dosing, the variability in PK parameters was high, with % CV ranging from 67.4-84% for C_{max} and 71.9-144% for AUC₁₂.

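### Do the relaxed evening fasts in Period 3 undermine the Day 5 food-effect ratio, so that a Day 1 contrast is needed?

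*Protocol*

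**What the plan says.** The food objective in Protocol 1.1 and 3 is "To evaluate the effect of food on the PK of multiple oral doses of sisunatovir". Its endpoint, repeated in SAP 2.2, is the ratio of AUCtau and Cmax on Day 5, with Tmax on Day 5.

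Protocol 6.1.1.2 sets the Period 3 fasts dose by dose:

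- **Day 1 and Day 5 mornings:** 10 h before and at least 4 h after.
- **Day 2-4 mornings:** "the pre-dose fasting period is 8 hours and the post-dose fasting period is a minimum of 1 hour".
- **Evenings:** "For evening doses, the pre-dose fasting period is 4 hours, and the post-dose fasting period is a minimum of 1 hour".

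Protocol 5.3.2 adds the meal times: "dinner will be provided approximately 13 hours after AM dosing (1 hour after PM dosing"; "During Period 3, lunch will be the first meal after an overnight fast of approximately 10 hours"; "Lunch will be provided approximately 4 hours after dosing".

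SAP 6.2.2 fits one mixed model of Treatment A (fed) against Treatment D (fasted) and does not repeat the day. Day 1 AUCtau and Cmax are derived and summarised by treatment and day with geometric means (SAP 6.2.1, Table 4), but no Day 1 ratio with a confidence interval is specified.

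**The concern.** Seven of the nine doses in the fasted period have a shorter fast than the two profiled mornings, and four of those seven are followed by dinner at about 1 h. The drug is absorbed slowly (Tmax 5-6 h in Protocol 2.2.4), so a meal at 1 h falls well before the expected peak and might act partly like food given with the dose. The drug also accumulates, so the Day 5 fasted profile contains material from those evening doses. If food raises exposure and a meal at 1 h carries part of that effect, the fasted denominator is inflated and the A/D ratio is pulled towards 1.

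Protocol 4.3 says the study data may help define dosing instructions for Phase 2/3. A near-null ratio could then be read as little food effect when part of it was dilution. Day 1 follows a strict fast and a washout, so a modelled Day 1 contrast looks like a cheap way to separate the two readings. SAP 6.2.2 not naming the day, and the different wording on Day 2-4 morning meals, add to the impression of a gap.

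**Working it through.** **Inputs.** Protocol 2.2.4: "resulting in a half-life of 7-10 hours in healthy participants"; Tmax 5-6 h; "resulting in 2-4 fold accumulation of exposure"; steady state after about 2 days; exposure more than dose proportional. Dosing is nine doses, 12 h apart. Prior single-dose fed/fasted AUC ratios are 162% (DIC) and 110.0% (DPB dispersed in water, 90% CI 85.6-141.4%).

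**Stated ratios reproduced.** 357/221 = 1.615 and 371/337 = 1.101. Both agree.

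**Evening-dose share of Day 5 AUCtau.** One compartment, first-order absorption, linear superposition:

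- k = ln 2 / half-life; ka solves Tmax = ln(ka/k)/(ka − k).
- Fraction of a dose's AUC by time t: F(t) = 1 − (ka·e^(−kt) − k·e^(−ka·t))/(ka − k).
- A dose given j intervals earlier contributes s_j = F(12(j+1)) − F(12j), for j = 0 to 8. Evening doses are j = 1, 3, 5, 7.

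| | Half-life 7 h, Tmax 5 h | Half-life 10 h, Tmax 6 h |
|---|---|---|
| ka (per h) | 0.354 | 0.329 |
| Day 5 morning dose | 58.2% | 45.4% |
| Evening doses | 31.9% | 37.9% |
| Earlier morning doses | 9.9% | 16.7% |
| Implied accumulation | 1.72 | 2.20 |

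Under the same model the evening share at the Day 5 peak is also 32-38%.

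**Why not a larger share.** Taking 4-fold accumulation as pure carry-over requires (1 − r^9)/(1 − r) = 4, so r = 0.775, and gives an evening share of 42%. But that r implies a half-life of 12·ln 2/(−ln 0.775) ≈ 33 h, against the stated 7-10 h. Only 1 − 0.775^4 = 64% of steady state would be reached after four doses, which does not fit the stated 2 days. Accumulation above about 2.2 more plausibly reflects non-linearity, part of which may belong to the Day 5 dose itself. The supported range is 32-38%, and non-linearity makes even that approximate.

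**Size of the dilution.** Let T be the strict-fast ratio, w the evening share, and g the fraction of the full food effect that a dinner at 1 h carries (unknown, 0 to 1). The Day 5 ratio reads T/(1 + w·g·(T − 1)). With w = 0.319 to 0.379:

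| T (AUC) | g = 0 | g = 0.5 | g = 1 |
|---|---|---|---|
| 1.10 (DPB in water) | 1.10 | 1.08 | 1.06-1.07 |
| 1.414 (upper limit of that CI) | 1.41 | 1.31-1.33 | 1.22-1.25 |
| 1.62 (DIC) | 1.62 | 1.45-1.47 | 1.31-1.35 |

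For Cmax at the DPB ratio of 1.077, g = 1 gives 1.05.

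**Against the precision.** The DPB interval has a half-width factor of √(141.4/85.6) = 1.285. Assuming 8-9 participants and 7-24 degrees of freedom, the SD of the log difference is 0.375-0.440. With n = 12 and 8-11 degrees of freedom the factor is 1.21-1.27. A move from 1.10 to 1.06-1.07 is 3-4%.

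**Would a Day 1 contrast separate the readings?** Day 1 AUC over 12 h is s_0, only 58% or 45% of the dose's total, so it responds to absorption rate as well as extent. As an assumption, let food delay Tmax with extent unchanged:

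| Delay | Day 1 AUCtau ratio | Day 5 AUCtau ratio |
|---|---|---|
| 1 h | 0.92-0.93 | 1.00 |
| 2 h | 0.83-0.85 | 1.00 |

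A true 1.10 with a 1 h delay would read about 1.10 × 0.92 = 1.01 on Day 1. That distortion of 7-8% exceeds the 3-4% it was meant to detect.

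**The case for a change.** The best case for acting is that a Day 1 model costs one extra run on parameters already derived, keeps Day 5 as the main contrast, and guards against a larger effect than expected. If the true ratio were 1.41, the lower confidence limit would be 1.414/1.27 = 1.11 to 1.414/1.21 = 1.17 undiluted. Under full dilution it would be 1.22/1.27 = 0.96 to 1.25/1.21 = 1.03. That difference could change how the result is read, and separate Day 1 summaries do not give a paired ratio with an interval.

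The arithmetic stands, but it stacks two assumptions: a ratio at the upper confidence limit, and a dinner at 1 h acting as a fully fed dose. Protocol 4.3 expects a minimal food effect for the study formulation. The 1.62 comes from a different formulation, and its own interval (83.0-316%) is very wide.

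The extra model also would not deliver what is asked of it. A Day 1 ratio that differs from Day 5 could reflect dilution, absorption delay, single-dose versus steady-state kinetics, or noise. Treatment D is always in Period 3, so Day 1 would share any period effect with Day 5.

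The remaining points are editorial. SAP 2.2 already assigns the food-effect ratio to Day 5. On Day 2-4 mornings, 6.1.1.2 gives a minimum post-dose fast, while 5.3.2 schedules the first meal at lunch. The wording differs, but a site that follows the lunch schedule also meets the minimum.

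**Conclusion.** No change to the plan is needed. The description of the fasted period is accurate: evening doses are followed by dinner at about 1 h and supply roughly 32-38% of Day 5 AUCtau. The Day 5 ratio is therefore fed dosing against the Period 3 regimen as given, not against a strict fast at every dose. That is a valid answer to the multiple-dose objective, and the fasting rules are stated openly enough for a report author to describe the result in those terms.

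Any understatement of a strict-fast effect ranges from none to a reading of 1.06-1.07 for a true AUC ratio of 1.10, well inside the expected interval. This rests on linear superposition, the stated half-life and Tmax, DPB-like variability, and an unknown influence of a meal 1 h after dosing. The shift would be material only if the true effect were much larger than the protocol expects and the later dinner carried most of it. Even then, a Day 1 AUCtau contrast would be a poor way to identify the cause. The Day 2-4 morning meal wording in 5.3.2 and 6.1.1.2 is a clerical matter to reconcile when the text is next revised; which rule applies is for the sponsor.

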6.1.1.3. Periods 4-7 (Cohort 1 only)

During Periods 4-7, participants will be assessing the taste of sisunatovir in a variety of vehicles using the questionnaire in [Appendix 10](#). Participants will taste 50 mg of sisunatovir in 7 ml of the following vehicles: water, saline, apple juice, and infant formula, given in a randomized order. Participants will swirl the study intervention in their mouth for 10 seconds and then spit it out. Participants will assess various aspects of the taste using the questionnaire in [Appendix 10](#): Oral Solution or Suspension Palatability Questionnaire at approximately 1 minute, 5 minutes, 10 minutes, and 20 minutes after spitting. There will be at least 60 minutes between tasting each study intervention, and at least 60 minutes after meals. Participants may eat plain crackers and water to cleanse their palate between assessments.

6.2. Preparation, Handling, Storage, and Accountability

1. The investigator or designee must confirm that appropriate conditions (eg, temperature) have been maintained during transit for all study interventions received and any discrepancies are reported and resolved before use of the study intervention.
2. Only participants enrolled in the study may receive study intervention and only authorized site staff may supply, prepare, and/or administer study intervention.
3. All study interventions must be stored in a secure, environmentally controlled, and monitored (manual or automated recording) area in accordance with the labeled storage conditions with access limited to the investigator and authorized site staff. At a minimum, daily minimum and maximum temperatures for all site storage locations must be documented and available upon request. Data for nonworking days must indicate the minimum and maximum temperatures since previously documented upon return to business.
4. Any excursions from the study intervention label storage conditions should be reported to Pfizer upon discovery along with actions taken. The site should actively pursue options for returning the study intervention to the labeled storage conditions, as soon as possible. Once an excursion is identified, the study intervention must be quarantined and not used until Pfizer provides permission to use the study intervention. Specific details regarding the excursion definition and information to report for each excursion will be provided to the site in the CRU procedures.
5. Any storage conditions stated in the SRSD will be superseded by the storage conditions stated on the label.
6. Study interventions should be stored in their original containers.

7. The investigator, institution, head of the medical institution (where applicable), or authorized site staff is responsible for study intervention accountability, reconciliation, and record maintenance (ie, receipt, reconciliation, and final disposition records), such as the IPAL or sponsor-approved equivalent. All study interventions will be accounted for using a study intervention accountability form/record.
8. Further guidance and information for the final disposition of unused study interventions are provided in the CRU's procedures. All destruction must be adequately documented. If destruction is authorized to take place at the investigator site, the investigator must ensure that the materials are destroyed in compliance with applicable environmental regulations, institutional policy, and any special instructions provided by Pfizer.

Upon identification of a product complaint, notify the sponsor within 1 business day of discovery as described in the IPM.

